APPENDIX 2. PARTIAL DATE CONVENTIONS

Imputed dates will NOT be presented in the listings.

ALGORITHM FOR TREATMENT-EMERGENCE OF ADVERSE EVENTS:

START DATE	STOP DATE	ACTION
Known	Known/Partial/ Missing	If start date < study med start date, then not TEAE If start date >= study med start date, then TEAE
Partial, but known components show that it cannot be on or after study med start date	Known/Partial/ Missing	Not TEAE
Partial, could be on or after study med start date OR Missing	Known	If stop date < study med start date, then not TEAE If stop date >= study med start date, then TEAE
	Partial	Impute stop date as latest possible date (i.e. last day of month if day unknown or 31st December if day and month are unknown), then: If stop date < study med start date, then not TEAE If stop date >= study med start date, then TEAE
	Missing	Assumed TEAE

Document: \\ieedc-vnasc01\BIOSdata\F2G\F901318\

Author:

Version Number:

3.0

Version Date:

06Apr2023

Template No.: CS_TP_BS016 Revision 6

Reference: CS_WI_BS005

Effective Date: 02Dec2019

F2G Ltd.
PROTOCOL F901318/0032

ALGORITHM FOR PRIOR, CONCOMITANT AND ANTIFUNGAL MEDICATIONS, AND NON-MEDICATION PROCEDURES:

START DATE	STOP DATE	ACTION
Known	Known	
If stop date < study med start date, assign as prior
 
If study med start date <= stop date <= end of treatment and start date < study med start date assign as both prior and concomitant
 
If study med start date <= start date <= end of treatment assign as concomitant
 
If start date > end of treatment, assign as post study

	Partial	
Impute stop date as latest possible date (i.e. last day of month if day unknown or 31st December if day and month are unknown), then:
 
If stop date < study med start date, assign as prior
 
If study med start date <= stop date <= end of treatment and start date < study med start date assign as both prior and concomitant
 
If study med start date <= start date <= end of treatment assign as concomitant
 
If start date > end of treatment, assign as post treatment

	Missing	
If start date < study med start date assign as both prior and concomitant
 
If study med start date <= start date <= end of treatment, assign as concomitant
 
If start date > end of treatment, assign as post treatment

Document: \\weedc-vnasc01\BIOSdata\F2G\F901318\ [Redacted]

Author: [Redacted] Version Number: 3.0

Version Date: 06Apr2023

Template No.: CS_TP_BS016 Revision 6 Reference: CS_WI_BS005

Effective Date: 02Dec2019

F2G Ltd.
PROTOCOL F901318/0032

START DATE	STOP DATE	ACTION
Partial	Known	
Impute start date as earliest possible date (i.e. first day of month if day unknown or 1st January if day and month are unknown), then:
 
If stop date < study med start date, assign as prior
 
If study med start date <= stop date <= end of treatment and start date < study med start date assign as both prior and concomitant
 
If study med start date <= start date <= end of treatment assign as concomitant
 
If start date > end of treatment, assign as post treatment

	Partial	
Impute start date as earliest possible date (i.e. first day of month if day unknown or 1st January if day and month are unknown) and impute stop date as latest possible date (i.e. last day of month if day unknown or 31st December if day and month are unknown), then:
 
If stop date < study med start date, assign as prior
 
If study med start date <= stop date <= end of treatment and start date < study med start date assign as both prior and concomitant
 
If study med start date <= start date <= end of treatment assign as concomitant
 
If start date > end of treatment, assign as post treatment

	Missing	
Impute start date as earliest possible date (i.e. first day of month if day unknown or 1st January if day and month are unknown), then:
 
If start date < study med start date assign as both prior and concomitant
 
If study med start date <= start date <= end of treatment assign as concomitant
 
If start date > end of treatment, assign as post treatment

Document: \\weedc-vnasc01\BIOSdata\F2G\F901318\ [Redacted]
 Author: [Redacted] Version Number: 3.0
 Version Date: 06Apr2023
 Template No.: CS_TP_BS016 Revision 6 Reference: CS_WI_BS005
 Effective Date: 02Dec2019

F2G Ltd.
 PROTOCOL F901318/0032

START DATE	STOP DATE	ACTION
Missing	Known	If stop date < study med start date, assign as prior If study med start date <= stop date <= end of treatment assign as both prior and concomitant If stop date > end of treatment, assign as concomitant Cannot be assigned as 'post treatment'
	Partial	Impute stop date as latest possible date (i.e. last day of month if day unknown or 31st December if day and month are unknown), then: If stop date < study med start date, assign as prior If study med start date <= stop date <= end of treatment assign as both prior and concomitant If stop date > end of treatment, assign as concomitant Cannot be assigned as 'post treatment'
	Missing	Assign as concomitant

Document: \\weedc-vnasc01\BIOSdata\F2G\F901318\ [Redacted]
 Author: [Redacted] Version Number: 3.0
 Version Date: 06Apr2023
 Template No.: CS_TP_BS016 Revision 6 Reference: CS_WI_BS005
 Effective Date: 02Dec2019

F2G Ltd.
PROTOCOL F901318/0032

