6.1 General Considerations

6.1.1 Schedule of Assessments

Day 1 is defined as the first day of administration of study drug. There is no Day 0; Day -1 is the day before administration of first dose of study drug, days preceding this are Day -2, Day -3, etc. Day 2 is the second day of administration of study drug, Day 3 is the third day of administration of study drug, etc.

Study assessments (visits) are scheduled in relation to days of administration of study drug. Screening assessments are to be completed within the 7 days prior to start of treatment unless otherwise specified and agreed with the MM. Assessments scheduled between Day 1 and Day 10 must be completed within the scheduled windows. Subsequent visits are permitted some flexibility to facilitate completion of the assessments; ± 2 days for the visits between study Day 14 and study Day 35 (Visits 8 to 12a) and ± 3 days at study Days 42, 49, 56, 70 and main study phase EOT (Visits 13 to 15, and 17). The Day 84 assessment (Visit 16) is permitted ± 6 days to allow treatment up to Day 90. The post-treatment FU visit (Visit 18) will be performed 4 weeks (± 7 days) after the last dose of study drug (this may not be the last patient visit). For patients planning to receive ET beyond Day 90, the Day 84 visit and the main study phase EOT visit will be combined into a single Day 84/EOS/EOT visit on approximately Day 90. Subsequent visits will be every 4 weeks to assess the safety of continued treatment and to assess the need for further treatment, and there will be a FU visit 4 weeks after ET is completed.

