6.4.1.1 Reporting of Adverse Events

All AEs which occur after the patient has provided informed consent, regardless of severity and whether or not they occurred during study enrolment, treatment or follow-up, are to be recorded on the appropriate AE pages (either ‘serious’ or ‘non-serious’) in the eCRF. The Investigator should complete all the details requested including dates of onset, severity, action taken, outcome and relationship to study drug. Each event should be recorded separately.

Each AE will be assessed to determine whether it meets seriousness criteria. If the AE is considered serious, the Investigator should record this event in the eDC system within 24 hours of becoming aware of the event. This entry into the eDC system will automatically trigger an e-mail alert to the Sponsor and to the MM.

An event may qualify for expedited reporting to regulatory authorities if it is an SAE, unexpected per reference safety information and considered related (Suspected Unexpected Serious Adverse Reaction [SUSAR]) in line with relevant legislation. All Investigators will receive a safety letter

notifying them of relevant SUSAR reports. The Investigator should notify the Ethics Committee as soon as is practical, of serious events in writing where this is required by local regulatory authorities, and in accordance with the local institutional policy.

Any SAE, including death due to any cause, which occurs during this study, whether or not related to the study drug, must be reported immediately (within 24 hours of the study centre's knowledge of the event) in the eCRF. The report will contain as much available information concerning the SAE to enable the Sponsor (or an authorized representative) to file a report, which satisfies regulatory reporting requirements.

If for any reason it is not possible to record the SAE information electronically, i.e., the eCRF database is not functioning, record the SAE on the paper SAE reporting form and submit within 24 hours as described above.

— As soon as it is possible to do so, any SAE reported via paper must be transcribed into the eCRF database according to instructions in the eCRF completion guidelines.

— If an SAE has been reported via a paper form because the eCRF database has been locked, no further action is necessary.

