8.2.4 Safety Endpoints

Descriptive statistics will be used to present the safety outcomes including:

- Changes in concurrent medication dose and/or frequency resulting from potential DDIs
- Hospitalisations
- Overall exposure, individual dose modification, dose intensity.
- Incidence of treatment-emergent and other (including but not limited to):
 - AEs
 - SAEs (including deaths)
 - AEs leading to death
 - Liver-related AEs
 - AEs leading to premature treatment discontinuation
 - AEs leading to premature study withdrawal
 - AEs by relationship

- AEs by severity (CTCAE grade)
- AESIs
- Change from baseline in clinical laboratory test results and incidence of pre-defined treatment-emergent abnormalities (CTCAE)
- Liver-related toxicity: Incidence and time-to-event analyses of elevations in ALT, AST, bilirubin, as described in detail in Section 6.4.2.3.
- Change from baseline in ECG results and incidence of pre-defined treatment-emergent abnormalities (CTCAE)
- Change from baseline in vital signs (including weight and BMI) and incidence of pre-defined treatment-emergent abnormalities (CTCAE)
- [REDACTED]
- Physical examination: Any abnormal clinically significant findings, as judged by the Investigator, will be listed in a by-patient data listing only.

A treatment-emergent AE (TEAE) is defined as any AE starting or worsening on or after the first dose of study drug up to and including last dose of study drug or during the post-treatment FU. Treatment-emergent AEs which occur in the main study phase or FU will be presented in the study report; TEAEs which occur in the ET phase or post-ET FU will be presented in the report addendum.

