18.1. ADVERSE EVENTS

Adverse Events will be coded using the most recent version of MedDRA.

- TEAEs will be presented by phase; TEAEs occurring in the main phase, TEAE's occurring in the extended phase, and TEAEs occurring in main or extended phase.

Document: \\weedc-vnasc01\BIOSdata\F2G\F901318 [REDACTED]
Author: [REDACTED] Version Number: 3.0
Version Date: 06Apr2023
Template No.: CS_TP_BS016 Revision 6 Reference: CS_WI_BS005
Effective Date: 02Dec2019

- TEAEs occurring in the main phase are defined as any AE which started or worsened on or after the first dose of main phase study treatment up to and including the post-treatment follow-up for the main phase.
- TEAEs occurring in the extended phase are defined as any AE which started or worsened on or after the first dose of extended phase study treatment up to and including the post-treatment follow-up for the extended phase. Note that if an AE occurred during the main phase, but worsened during the extended phase, the event qualifies as occurring in both main and extended phase. TEAEs occurring in main or extended phase are defined as any AE which started or worsened on or after the first dose of main phase study treatment up to and including the post-treatment follow-up for the extended phase.

See [appendix 2](#) for handling of partial dates for AEs. In the case where it is not possible to define an AE as treatment-emergent or not, the AE will be classified by the worst case; i.e. treatment-emergent.

A table listing the TEAEs with overall frequency >3% by preferred term in decreasing order of number of subjects with at least one TEAE in the preferred term will be presented.

Listings will include TEAEs and Non-TEAEs.

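### SAP Appendix 2 has no worsening test for adverse events known to start before first dose, and no end date, so it conflicts with the TEAE definition in SAP 18.1 and protocol 8.2.4

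*SAP*

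**What the plan says.** The definition appears twice. Protocol 8.2.4 describes a TEAE as "any AE starting or worsening on or after the first dose of study drug", and SAP 18.1 describes a main-phase TEAE as "any AE which started or worsened on or after the first dose of main phase study treatment". Both close the window at the post-treatment follow-up. For the extended treatment (ET) phase, SAP 18.1 adds a rule on worsening: "if an AE occurred during the main phase, but worsened during the extended phase, the event qualifies as occurring in both main and extended phase".

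SAP Appendix 2 then gives a decision table for treatment emergence. Its first row takes known start dates, whatever the stop date, and rules "If start date < study med start date, then not TEAE". Its second row takes start dates described as "Partial, but known components show that it cannot be on or after study med start date" and also returns not TEAE. Only an ambiguous or missing start date goes on to the stop date, with the rule "If stop date >= study med start date, then TEAE"; a missing stop date is assumed to be a TEAE. No row mentions worsening, and no row has an upper limit.

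Pre-dose events will be in the database, because protocol 6.4.1.1 requires recording of "All AEs which occur after the patient has provided informed consent". SAP 3.3, which lists departures from the protocol analysis, does not mention removing worsening from the TEAE definition.

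**The concern.** The SAP states one definition in its text and a different rule in its algorithm. Two programmers, one working from SAP 18.1 and one from Appendix 2, would classify the same record differently.

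The classification feeds every TEAE summary in SAP 18.1: overall incidence, maximum severity, relationship, serious and fatal events, events leading to discontinuation or dose adjustment, and events of special interest. Describing safety is a secondary objective, and there is no control arm against which an undercount or overcount would cancel. A screening-period event that becomes more severe on drug is exactly what the words about worsening are there to catch.

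**Working it through.** The plan gives no figure to reproduce, so the check compares two rules. Day 1 is first dose, and the event days are illustrative.

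**Rule A (Appendix 2)**
- Known start: TEAE if start ≥ Day 1, otherwise not.
- Partial start that must be pre-dose: not TEAE.
- Ambiguous or missing start: TEAE if stop ≥ Day 1 or stop is missing, otherwise not.

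**Rule B (start side of SAP 18.1 and protocol 8.2.4)**
- TEAE if start ≥ Day 1 or worsening ≥ Day 1.

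| Start date as recorded | True course | Rule A | Rule B |
|---|---|---|---|
| Known | Starts Day -3, worsens Day 10, stops Day 20 or stop missing | Not TEAE | TEAE (conflict) |
| Partial, must be pre-dose | Same | Not TEAE | TEAE (conflict) |
| Ambiguous or missing | Same | TEAE | TEAE |
| Known, or partial and must be pre-dose | Starts Day -3, no worsening, stops Day 20 | Not TEAE | Not TEAE |
| Ambiguous or missing | Starts Day -3, no worsening, stops Day 20 | TEAE | Not TEAE |
| Known, ambiguous or missing | Starts Day 5, with or without worsening on Day 10, stops Day 20 | TEAE | TEAE |

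The first two lines are the problem. The fifth line errs towards inclusion and fits the worst-case approach that SAP 18.1 announces for events that cannot be classified.

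**Exposure window.** The affected events begin between consent and first dose. Protocol 6.1.1 sets the scale: "Screening assessments are to be completed within the 7 days prior to start of treatment", unless otherwise specified and agreed with the Medical Monitor.

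**Upper limit.** Take a patient with a successful outcome who stops treatment on Day 20.
- The follow-up visit is due at 20 + 28 = Day 48, with a ±7-day window of Day 41 to Day 55.
- The patient still returns for Day 84 (window Day 78 to Day 90). Protocol 5.1 says that the follow-up visit may precede Day 42 or Day 84.
- Protocol 6.4.1.3 covers events observed up to end of study, which is the last assessment that the patient completes. An event starting on Day 70 can therefore be recorded.
- Rule A: 70 ≥ 1, so TEAE. Definition: 70 > 55, so outside the window.

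The medication table in the same appendix does use end of treatment as a boundary, so the omission is particular to the adverse event table.

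**The case against.** The best reply is that Appendix 2 deals with partial dates. Its title says so, and SAP 18.1 refers to it only for that purpose, so the text would define a TEAE and the appendix would merely resolve incomplete dates. The documents state no order of precedence, and a programmer could well follow 18.1. But the table is headed as the algorithm for treatment emergence, and its first row classifies complete dates. The conflict is therefore on the page. The worst-case fallback does not remove it, because it applies only when status cannot be determined, and here the table determines it.

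The second reply concerns data entry. Protocol 6.4.1 counts worsening of a pre-existing condition as an adverse event, and 6.4.1.1 asks for each event to be recorded separately. If a site opens a new record at worsening, its start date falls on treatment and passes the algorithm. This stands as a condition on the size of the problem. It does not settle the matter, because no section requires a new record. Protocol 8.9.2, which takes the worst severity when intensity changes, can be read either way.

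A reader might go further and infer three things that the documents do not support:

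- **That main-phase events worsening in ET are lost from the ET tables.** Appendix 2 tests a single study medication start date and assigns no phase. A main-phase event passes it as a TEAE, and SAP 18.1 then counts it in both phases if it worsens.
- **That the hepatic safety review would miss cases.** Exclusion 13 keeps out marked liver test abnormality at screening. Protocol Appendix 3 requires moderate and major enzyme elevations, defined with reference to baseline, to be reported as events of special interest. Protocol 6.4.4.3 sends narratives of all hepatic events of special interest to the Hepatic Advisory Committee. SAP 18.2 tabulates laboratory shifts from baseline without using event start dates.
- **That the events disappear.** SAP 18.1 keeps events that are not TEAEs in the listings.

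**Conclusion.** The conflict is real but minor. For known pre-dose start dates, and partial dates that must be pre-dose, Appendix 2 returns not TEAE for an event that SAP 18.1 and protocol 8.2.4 count if it worsened on drug. The known-start row also admits events that start after the definition's window has closed. The first error lowers TEAE counts and the second raises them.

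The size cannot be computed, because the documents give no count of screening-period events or of events after follow-up. The undercount is probably small: it is mainly limited to events starting in a screening period of about 7 days. It assumes that the program follows the Appendix 2 table and that the worsening stays on the original record. The overcount assumes that treatment stopped early enough for a later study visit to fall after the follow-up visit.

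**What to change.** Amend SAP Appendix 2 in three places.

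1. In both pre-dose rows, add that the event is a TEAE if its severity or seriousness increased on or after first dose. Severity should mean CTCAE grade or, where CTCAE does not apply, the mild/moderate/severe scale in protocol 6.4.1; a test on CTCAE grade alone would miss the latter events. The alternative is to state that each worsening is entered as a new adverse event record with its own start date. The first option needs a date for the change in severity or seriousness, and the documents do not show that one is collected, so check this before choosing.
2. Add that an event starting after the end of the phase's post-treatment follow-up is not a TEAE. Patients who enter ET have no main-phase follow-up visit (SAP 3.1), so the text should name the closing point of the main phase for them.
3. State that phase allocation, including worsening during ET, follows SAP 18.1.

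The cost is SAP wording and one extra derivation. TEAE counts may change slightly in either direction: up from the worsening test, down from the upper limit.

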12. MEDICATIONS

Concomitant and prior Antifungal Medications will be coded using the most recent version of World Health Organisation Drug Dictionary (WHO-DD) and descriptive statistics by ATC level 4 for all concomitant medications

Document: \\weedc-vnasc01\BIOSdata\F2G\F901318\ [Redacted]
Author: [Redacted] Version Number: 3.0
Version Date: 06Apr2023
Template No.: CS_TP_BS016 Revision 6 Reference: CS_WI_BS005
Effective Date: 02Dec2019

and antifungal concomitant medications based on the ITT analysis set will be presented.

See [appendix 2](#) for handling of partial dates for medications, in the case where it is not possible to define a medication as prior, concomitant or post the medication will be classified by the worst case; i.e. concomitant. A medication may be classed as both 'prior' and 'concomitant'.

- 'Prior' medications are medications which were started prior to the first dose of study medication.
- 'Concomitant' medications are medications which were:

started prior to, on or after the first dose of study medication but prior to last dose of study medication,

AND ended on or after the date of first dose of study medication or were ongoing at the end of the study.

- 'Post' medications are medications started after the last dose of study medication (to be listed only).
- Therapeutic drug monitoring data on medications resulting in dose adjustments will be listed.
- Concomitant antifungal usage (Yes/No)
 - number of days of concomitant antifungal usage on study
- Summary will be presented by systemic antifungal medication and non-antifungal medications. Systemic antifungals will be confirmed and provided by medical review process.
- Plot for duration of antifungal medications will also be presented.

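### SAP Appendix 2 has no branch for a medication or procedure that starts before first dose and stops after end of treatment, although SAP 12 makes such a record both prior and concomitant

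*SAP*

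**What the plan says.** SAP 12 defines the classes by date. Prior medications are "medications which were started prior to the first dose of study medication", with no condition on the stop date. Concomitant medications must start before the last dose, and the second limb is "AND ended on or after the date of first dose of study medication or were ongoing at the end of the study", with no upper limit on the stop date. SAP 12 allows one medication to be in both classes. A medication that cannot be placed is counted as concomitant. SAP 13 uses matching definitions and the same fallback for procedures.

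Appendix 2 turns this into a three-by-three grid: start date known, partial or missing, against stop date known, partial or missing. In the Known/Known, Known/Partial, Partial/Known and Partial/Partial cells, after any imputation, there are four conditions:

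- stop before first dose: prior;
- for a record already running at first dose: "If study med start date <= stop date <= end of treatment and start date < study med start date assign as both prior" (the line then adds the concomitant class);
- for a start on treatment: "If study med start date <= start date <= end of treatment assign as concomitant";
- start after end of treatment: post.

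The other cells treat a long-running record differently. With a missing stop date the rule is "If start date < study med start date assign as both prior and concomitant". With a missing start date it is "If stop date > end of treatment, assign as concomitant". With both dates missing the record is concomitant.

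**The concern.** The second condition is the only one that could catch a record already running at first dose, and it caps the stop date at end of treatment. A record that runs past that point has nowhere to go, even though it overlaps the whole treatment course and SAP 12 places it without difficulty.

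Such records will occur. Protocol 5.9 and 6.2.6 collect medications before study entry and through the four-week post-treatment period, so stop dates after end of treatment will be recorded. Imputation can add more: Appendix 2 moves a stop date known only by month to the month's end, and one known only by year to 31 December.

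This is a single-arm study. Protocol 5.9.2.1 discourages, but permits, other systemic antifungals because they cloud the reading of efficacy. The SAP 12 summaries of whether a patient used a concomitant antifungal, and for how many days, are how a reader judges that. Protocol 8.7 also requires medications and procedures to be categorised by date, which an unassigned record fails.

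**Working it through.** The plan gives no figure to reproduce, so the check is of logic. I coded the four Appendix 2 conditions and the SAP 12 definitions side by side.

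**Inputs.** The conditions and definitions are as described above. For illustration only, first dose is day 10, and both end of treatment and last dose are day 100. Start days run from 1 to 120, and stop days from the start day to 130.

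**The six possible orderings, one example each:**

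| Start | Stop | Appendix 2 | SAP 12 |
|---|---|---|---|
| 5 (before first dose) | 8 (before first dose) | prior | prior |
| 5 (before first dose) | 50 (on treatment) | prior and concomitant | prior and concomitant |
| 5 (before first dose) | 120 (after end of treatment) | **none** | prior and concomitant |
| 50 (on treatment) | 60 (on treatment) | concomitant | concomitant |
| 50 (on treatment) | 120 (after end of treatment) | concomitant | concomitant |
| 110 (after end of treatment) | 120 (after end of treatment) | post | post |

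The third row against each condition:

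1. Stop before first dose? 120 < 10 is false.
2. Stop between first dose and end of treatment, with an earlier start? 10 <= 120 <= 100 is false.
3. Start on treatment? 10 <= 5 is false.
4. Start after end of treatment? 5 > 100 is false.

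**Whole grid.** The number of pairs with start before day 10 and stop after day 100 is 9 start days × 30 stop days = 270. The number left unassigned by Appendix 2 is also 270, and every one has that pattern. SAP 12 classifies all 270 as both prior and concomitant.

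**Neighbouring cells.** The same record (start day 5) with the stop date missing is both prior and concomitant under Appendix 2. With the start date missing and stop day 120 it is concomitant. The gap is therefore confined to the four cells where both dates are available.

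**A boundary difference.** A record starting exactly on day 100 is concomitant under Appendix 2. It is in no class under SAP 12, which asks for a start strictly before the last dose and reserves the post class for starts after it. This is separate from the main point.

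**The case against.** The strongest reply is that SAP 12 already answers the question. Its definitions are complete for these records, it sends the reader to Appendix 2 only for partial dates, and the appendix title says the same. A programmer who works from SAP 12 gets the right answer. One who relies only on the fallback still keeps the record in the concomitant summaries. A record is lost from those only if the appendix is coded alone and both the definitions and the fallback are ignored.

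Most of that stands, and it limits the consequence. It does not close the gap. The appendix has its own Known/Known row, and for partial dates it is the stated rule. The fallback follows the sentence on partial dates, so its reach to fully dated records is unclear. Where it applies, it drops the prior class that SAP 12 requires. Two programmers could reasonably produce different flags.

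A reader might infer more than the documents support:

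- *That drugs taken throughout treatment disappear.* Those with a missing stop date, which would cover a drug recorded as ongoing, are assigned to both classes. Only a recorded or imputed stop after end of treatment is exposed.
- *That a table of prior medications is depleted.* SAP 12 names descriptive statistics for concomitant medications and concomitant antifungals. It mentions prior antifungals for coding but does not clearly specify a prior-medication table.
- *That efficacy subgroups are affected.* SAP 7.4 derives duration of prior antifungal therapy from start and stop dates, and prior response comes from the eCRF. Neither uses this flag.
- *That the pharmacokinetic groups by CYP inhibitor or inducer are affected.* SAP 17.1.1 does not say that it uses this flag.

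**Conclusion.** The omission is real and contradicts the SAP's own definitions: one ordering of six, in four cells of nine. It is a minor specification defect. Coded literally, an affected record has no category; with the fallback it is concomitant only; under SAP 12 it is both.

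The exposure is the descriptive medication and procedure summaries, including concomitant antifungal use and its days, and only if the appendix is programmed as written. The primary endpoint is the adjudicated response at Day 42 and does not use these flags.

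How many records are affected cannot be derived from the documents. They give no frequency for medications that span the whole course with a stop date, nor for partial stop dates. The logical result does not depend on the illustrative days chosen, only on first dose preceding end of treatment.

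**What to change.** In the Known/Known, Known/Partial, Partial/Known and Partial/Partial cells of Appendix 2, replace the second condition with: *If start date < study med start date and stop date >= study med start date, assign as both prior and concomitant.* This matches SAP 12. It classifies all 270 unassigned pairs in the grid and leaves the other five orderings unchanged. Because it sets no upper limit on the stop date, it gives the same answer whether end of treatment is read as the main phase or the extended phase.

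The cost is one condition in the SAP text and in the classification program. No new data or analysis is needed.
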